4.8. Bias

4.8.1. Confounding

Confounding will be handled by using propensity score (PS) methods. In addition, the use of an active comparator design reduce confounding by indication, as most users of the comparator are also likely to have hypertension as the indication for treatment. To further reduce confounding by indication, we will repeat the analyses after restriction to patients without history of heart or kidney disease, which are other indications for ACE-I/ARB use. Although we included a large number of coexisting conditions, life-style factors and co-medication, we cannot exclude the impact of unmeasured confounding, e.g., by severity of condition indication ACE-I/ARB treatment. As we lacked detailed data on severity of heart and renal diseases, we reduced confounding in a subgroup analysis of patients without any history of these diseases.

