4.8.1.1. Propensity score methods

The PS is the probability of being exposed given the covariate pattern for the patient. The PS will be estimated for each patient hospitalization in each of the examined comparisons using a logistic regression model including calendar time and the covariates listed in the Appendix. As we are interested in the average treatment effect in the treated (ATT), we apply PS-weighting using ATT weights to make the number and covariate distribution in the comparison groups resemble that of the ACE-I/ARB users.

8

Overlap in PS distributions will be checked before weighting. Covariate balance will be assessed by standardized differences (SDs), empirical cumulative distribution functions for continuous variables (age and index), and by PS-weight percentiles.

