4.9. Statistical analyses

In the analyses of prognosis, patients will be followed from day of SARS-CoV-2 positive test result and until date of hospital admission, ICU admission (in analysis of ICU admission), date of death, end of follow-up or for up to 30 days.

Patient characteristics will be tabulated according to each exposure group.

Descriptive analyses will explore the timing of outcomes one month prior to and three months after the first positive test for SARS-CoV-2. In case of a substantial fraction of outcomes having occurred in the days leading up to a positive test, a post-hoc analysis with a larger follow up windows (pre- and post-test) will be conducted.

For each exposure group, we will estimate the 30-day PS-weighted cumulative incidence (risk) of of death, and of each of the non-fatal events (hospital admission, ICU admission, ICU+MV, ICU+inotropes/vasopressors, RRT) accounting for competing risk by death. All 95% confidence intervals will be computed using bootstrapping. The risk of each outcome within 30 days will be computed with 95% CI.

Propensity scores for each comparison (e.g. current ACE-I/ARB use vs. current CCB use) will be computed using logistic regression including all the potential confounders as described above. All other exposures (anti-hypertensive drugs) will be included in the PS-model. The propensity score weighted (SMRW=ATT) cumulative incidence (risk) of each outcome will be plotted and estimated with 95% CI estimated by bootstrapping. The adjusted (PS weighted) risk difference will be computed for the 0-30 period.

The 30-day risk will be compared using PS weighted log binomial regression to estimate risk ratio for death, hospital admission, ICU admission, ICU+MV, RRT, and ICU+inotropes/vasopressors.

Subgroup analysis will be conducted to address effect modifiers including age group (=<65, >65 years) and in patients with assumed uncomplicated hypertension as the primary indication for treatment, defined as patients without any history of diabetes, renal disease, angina pectoris, myocardial infarction, or heart failure. We will also stratify by ABO blood type, if available, because blood type is suggested to be associated with ACE2.³⁰

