Acute renal replacement therapy (RRT) (in patients without chronic RRT)	DNPR/Procedure		BJFD0	BJFD2 (any codes within prior 12 months)
Treatment with inotropes/vasopressors	DNPR/Procedure		BFHC92A, BFHC92B, BFHC92C, BFHC92D, BFHC92E, BFHC93A, BFHC93B, BFHC93C, BFHC95	
Covariates				
Age	CPR			
Sex	CPR			
Calendar time (before / after lockdown)	DNPR			
Hospital-diagnosed hypertension	DNPR/ICD-10	10y	110, 115	
Stable angina pectoris (without procedures)	DNPR/ICD-10	10y	120, 1251, 1259	121, 122, 123, 1200
Stable angina pectoris or CABG/PCI procedures	DNPR/ICD-10	10y	120, 1251, 1259	121, 122, 123, 1200
	DNPR/Procedure	10y	KFNA, KFNB, KFNC, KFND, KFNE, KFNF, KFNG, KFNH20	I21, I22, I23, I200 (any diagnosis during hospital contact with
				contact the proc

				or within 10
				years before
Myocardial infarction	DNPR/ICD-10	10y	121, 122, 123	
Heart failure	DNPR/ICD-10	10y	150	
Stroke	DNPR/ICD-10	10y	160, 161, 163, 164	
Atrial fibrillation/flutter	DNPR/ICD-10	10y	148	
Heart valve disease	DNPR/ICD-10	10y	105, 106, 107, 108, 109.8, 134-137, 139, 151.1A, Q22, Q23	
Venous thromboembolism	DNPR/ICD-10	10y	126, 1801, 1802, 1803	
Diabetes	DNPR/ICD-10	10y	E10, E11, E12, E13, E14, O24, G63.2, H360, N083	O24.4
	NPD/ATC	10y	A10A, A10B	
Chronic pulmonary disease	DNPR/ICD-10	10y	J40, J41-J44, J45–J47, J60–J67, J68.4, J70.1, J70.3, J84.1, J92.0, J96.1, J98.2, J98.3	
Markers of smoking (diagnoses or medications for tobacco smoking or	DNPR/ICD-10	10y	J41-J44, F17, Z716, Z720	
chronic obstructive pulmonary disease)				
	NPD/ATC	10y	R03, N07BA	
Obesity diagnoses or medications	DNPR/ICD-10	10y	E66	
	NPD/ATC	10y	A08	
Alcoholism-related diagnoses or medication for alcohol deterrent	DNPR/ICD-10	10y	DF10, DE244, DG312, DG621, DG721, DI426, DK292, DK70, DK852, DK860, DQ860, DZ502, DZ714, DZ721	F100
	NPD/ATC	10y	V03AA, N07BB	
Kidney disease diagnosis	DNPR/ICD-10	10y	112, 113, N00–N05, N07, N11, N14, N18–N19, Q61, N08, E102, E112, E142	
End-stage renal disease (kidney transplant or dialysis)	DNPR/Procedure	10y	BJFD2	
	DNPR/Surgery	10y	KKAS	
	DNPR/ICD-10	10y	T861, Z940	
Liver disease	DNPR/ICD-10	10y	B18, B150, B160, B162, B190, I85, K70, K71, K72, K73, K74, K760, K76.6	
Dementia	DNPR/ICD-10	10y	DF00, DF01, DF02, DF03, DG30, DG310B, DG311, DG318, DG319	
	NPD/ATC	10y	N06D	
Cancer (including metastatic cancer)	DNPR/ICD-10	10y	C00-C96, D459, D46, D471, D473, D474, D475, CxxxM	C44
Concurrent antihypertensive medication (see exposures)	NPD/ATC			

Statins	NPD/ATC	90d	C10AA, C10B

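### The Appendix code table puts I11 in no covariate row and I13 only under kidney disease, so some patients with hypertensive heart disease score as having neither hypertension nor heart failure

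*Protocol*

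**What the plan says.** All references are to the protocol. In the copy reviewed, the PDF reader turned the letter I into the digit 1 in many ICD-10 codes, so 150 below stands for I50.

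- **Hypertension.** The row "Hospital-diagnosed hypertension" lists two codes, I10 and I15, with a 10-year look-back.
- **Heart failure.** The row has one code: "Heart failure DNPR/ICD-10 10y 150".
- **Kidney disease.** The row reads "112, 113, N00–N05, N07, N11, N14, N18–N19, Q61, N08, E102, E112, E142". It is the only row that contains I12 or I13.
- **Valve disease.** The row reads "105, 106, 107, 108, 109.8, 134-137, 139, 151.1A, Q22, Q23". Like the angina, myocardial infarction and atrial fibrillation rows, it contains neither I11 nor I13.
- **Where the rows are used.** Section 4.8.1.1 specifies a "logistic regression model including calendar time and the covariates listed in the Appendix". Section 4.9 adjusts the test-negative logistic models for the same covariates.
- **Restricted analyses.** Section 4.9 has a subgroup with presumed uncomplicated hypertension, "defined as patients without any history of diabetes, renal disease, angina pectoris, myocardial infarction, or heart failure". Section 4.8.1 plans a "restriction to patients without history of heart or kidney disease, which are other indications for ACE-I/ARB use". Neither has a code list of its own.

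**The concern.** In ICD-10, the classification that the table names, I11 is hypertensive heart disease, I11.0 is the form with heart failure, and I13 is hypertensive heart and renal disease. Hypertension and heart failure are both indications for ACE-I/ARB and plausible predictors of death from COVID-19. If some patients who have these conditions score as free of them, the covariates carry error into the weighting and into the test-negative models. Patients with recorded heart failure can also stay in a subgroup that the plan uses because it should contain none. Section 4.8.1 relies on restriction precisely because the severity of heart and renal disease is not measured, so a leak there weakens the safeguard.

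**Working it through.** **Step 1. Is the hypertension entry a range?** Other entries in the same column keep their dash where a range is meant (N00–N05 in the kidney row, 134-137 in the valve row). The hypertension entry is separated by a comma. It reads as I10 and I15, not as I10 to I15.

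**Step 2. Match each code by prefix against the ICD-10 covariate rows.**

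| Code | Row that captures it |
|---|---|
| I10, I15 | hypertension |
| I11, I11.0, I11.9 | none |
| I12 | kidney disease only |
| I13, I13.0, I13.2 | kidney disease only |
| I50 | heart failure |

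**Step 3. Follow a patient with no I10, I15 or I50 code in the 10 years before the test and no other excluding condition.**

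| Only relevant code | Hypertension | Heart failure | Kidney disease | 4.9 subgroup | 4.8.1 restriction, if built from the Appendix rows |
|---|---|---|---|---|---|
| I11.0 | 0 | 0 | 0 | enters, against its definition | enters |
| I11.9 | 0 | 0 | 0 | enters, no breach of its definition | enters |
| I13 | 0 | 0 | 1 | removed | removed |

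**Step 4. Does the table have a convention for codes that denote two conditions?** Yes, it usually counts them twice. E102, E112 and E142 fall under kidney disease and, through E10, E11 and E14, under diabetes. N083 falls under diabetes and, through N08, under kidney disease. K70 is under both alcoholism and liver disease. J41-J44 is under both pulmonary disease and smoking. I12 and I13 were placed in the kidney row but not repeated under hypertension, and nothing parallel was done for hypertensive heart disease. No reason is given.

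**Step 5. Possible size.** The documents give no I11 prevalence, so every prevalence and mortality ratio here is an assumption. From section 4.10, expected ACE-I/ARB users are 0.17 × 7,515 = 1,278. If 0.5% to 3% of them have I11 without I10, I15 or I50, that is 6 to 38 patients.

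For a wholly uncontrolled binary confounder with prevalence p1 in users and p0 in comparators, and mortality ratio R, the bias factor on the RR is [1 + p1(R − 1)] / [1 + p0(R − 1)].

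- p1 = 0.5%, p0 = 0.1%, R = 2: 1.005/1.001 = 1.004
- p1 = 1%, p0 = 0.2%, R = 3: 1.020/1.004 = 1.016
- p1 = 2%, p0 = 0.3%, R = 3: 1.040/1.006 = 1.034
- p1 = 3%, p0 = 0.5%, R = 4: 1.090/1.015 = 1.074
- p1 = p0, any R: 1.000
- the fourth case with the prevalences swapped: 1.015/1.090 = 0.931

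The last two lines show that both size and direction come from the assumed gap between the groups.

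**Step 6. Compare with sampling error.** At the plan's 4% mortality, 1,278 users give about 51 deaths, and the other 0.83 × 7,515 = 6,237 patients give about 249. The crude standard error of log RR is √(1/51 − 1/1,278 + 1/249 − 1/6,237) ≈ 0.15, before any loss from weighting. The largest assumed factor, ln(1.074) = 0.07, is under half of that.

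**The case against.** The strongest reply is that very little is at stake.

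- **Few patients may be affected.** The error needs an I11 or I13 code with no I10, I15 or I50 in ten years. Nothing in the documents shows how often hospitals code that way. This stands, and it limits the point to those patients. A reader might infer that everyone with I11 or I13 is misscored, but the table does not support that.
- **Such patients are not invisible to the models.** Loop diuretics, concurrent antihypertensives, number of antihypertensives, statins, atrial fibrillation, valve disease, kidney disease and age are all covariates and act as partial proxies. This stands. The factors in Step 5 ignore that adjustment, so they tend to overstate what remains under each assumption.
- **I13 matters less.** These patients score kidney disease = 1, and the kidney criterion removes them from both restricted analyses. This stands. Only their hypertension and heart failure covariates are wrong.
- **The 4.9 subgroup does not exclude all heart disease.** It names five conditions, and I11 without heart failure is not one of them. This stands. Only I11.0 contradicts the definition.
- **The 4.8.1 restriction has no code list and may be defined elsewhere.** This stands as a condition: the leak follows only if the Appendix rows, the only list given, are used.
- **The plan already admits unmeasured confounding.** That does not answer the point, because here the diagnosis is recorded and the code list drops it.

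**Conclusion.** The gap is real and lies in the protocol's own code list, so it is not a detail left to a later document. As written, patients with I11 and no I10, I15 or I50 code in the look-back score 0 for hypertension and heart failure in the propensity score and the test-negative models. Those coded I11.0 enter the 4.9 subgroup despite a named exclusion. All I11-only patients enter the 4.8.1 restriction if it is built from the Appendix rows. I13-only patients are misscored on two covariates and nothing more.

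The effect on the estimates is probably small. A reader might infer from Step 5 that the death RR is inflated by up to 7%, towards apparent harm. The documents do not support that. The prevalences and mortality ratios are assumed, the proxies are ignored, and against CCB users, a comparator chosen for similar indications, the prevalence gap could be near zero or reversed. The conclusion rests on reading the hypertension entry as two codes and on the ICD-10 meanings of I11 and I13, which the protocol does not spell out. The correction is worth making because it is cheap and makes the restricted analyses match their descriptions, not because a material bias has been shown.

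**What to change.** In the Appendix code table:

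1. Add I11, I12 and I13 to hospital-diagnosed hypertension. Keep I12 and I13 under kidney disease as well, in line with the table's practice for codes that denote two conditions.
2. Add I11.0, I13.0 and I13.2 to heart failure.

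Then use the revised heart failure codes for the exclusion in the section 4.9 subgroup. In section 4.8.1, state which codes define heart disease for the restriction, and count I11 among them.

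The cost is a few extra codes on diagnosis data already linked, with no change of design. The restricted groups become slightly smaller. Reporting the number of patients reclassified would show whether the gap mattered.

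### I200 (unstable angina) is an exclusion code in both angina rows of the code table and an inclusion code in none, so some of these patients can have no coronary flag in the propensity score and test-negative models

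*Protocol*

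**What the plan says.** The table headed Codes, which sections 4.8.1.1 and 4.9 call the Appendix, has three coronary rows, all with a 10-year look-back.

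- Two rows concern stable angina. One has no procedure codes; the other is labelled "Stable angina pectoris or CABG/PCI procedures". The diagnosis lines of both include I20, I251 and I259, and both list as exclusion codes "121, 122, 123, 1200". The leading letter I has been read as the digit 1 there; the procedure line prints the same codes correctly.
- The CABG/PCI procedure line has its own exclusion: "I21, I22, I23, I200 (any diagnosis during hospital contact with" the procedure, or in the 10 years before. The cell is broken across lines, but this is its evident sense.
- The third row, "Myocardial infarction", includes I21, I22 and I23 only.

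Section 4.8.1.1 estimates the propensity score "using a logistic regression model including calendar time and the covariates listed in the Appendix". Section 4.9 adjusts the test-negative models for the same list.

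The uncomplicated-hypertension subgroup in section 4.9 is "defined as patients without any history of diabetes, renal disease, angina pectoris, myocardial infarction, or heart failure". Section 4.8.1 states that "we will repeat the analyses after restriction to patients without history of heart or kidney disease". Neither sentence gives codes.

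**The concern.** Patients excluded from the angina rows because of I21-I23 come back through the infarction row. Patients excluded because of I200 come back nowhere, and there is no row for unstable angina or for ischaemic heart disease as a whole. The list thus flags stable angina and infarction and skips the condition between them.

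Coronary disease plausibly bears on both ACE-I/ARB prescribing and 30-day mortality, so it is a confounder that the plan means to control. A gap here enters the weighting for the primary mortality comparison as well as the test-negative odds ratios. The balance checks in section 4.8.1.1 cannot reveal it, because standardised differences are computed only for covariates that exist.

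Section 4.8.1 also offers the restriction to patients without heart or kidney disease as the answer to missing data on severity. That purpose is weakened if some patients with the less stable form of angina remain in.

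**Working it through.** The protocol states no figure on this point, so there is nothing to reproduce. The check is on the logic of the code lists, followed by a rough scale.

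**Step 1: test patients.** The column of exclusion codes can be read in two ways. At patient level, any excluded code removes the patient from the row. At code level, only the excluded code is ignored. The patient-level reading is the more natural one: I21-I23 are not sub-codes of I20, I251 or I259, so listing them would do nothing at code level. The resulting coronary flags are:

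| Codes in the look-back | Patient level | Code level |
|---|---|---|
| I200 only | none | none |
| I200 at or before PCI/CABG, no other coronary code | none | none |
| I200 with I209 or I251 | none | stable angina |
| I200 with any of I21-I23 | infarction | infarction |
| I200 with I50 | none (heart failure flagged) | none (heart failure flagged) |
| I209, no I200 | stable angina | stable angina |
| PCI/CABG, with I200 recorded only afterwards | procedure flag kept | procedure flag kept |

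The last row follows from the timing in the procedure line and assumes no excluded code at or before the procedure. The first two rows lose every coronary flag under either reading; the third does so only at patient level.

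**Step 2: text against table.** Section 4.9 speaks of angina pectoris without the word stable. Read literally, that excludes I200. The only angina codes in the protocol are the two stable-angina rows, which leave I200 out. Built from the table, the subgroup keeps these patients; built from the words, it has no code list for angina. The same applies to the coronary part of heart disease in section 4.8.1.

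**Step 3: rough count.** The protocol gives no prevalence of I200. Assume, for illustration only, that 0.2% to 3% of test-positive patients have I200 and no I21-I23 code. Section 4.10 gives 7,515 positives and an expected 17% on ACE-I/ARB.

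- All positives: 7,515 × 0.002 = 15 to 7,515 × 0.03 = 225.
- ACE-I/ARB users at the same prevalence: 15 × 0.17 = 3 to 225 × 0.17 = 38.

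**Step 4: rough bias.** Let f1 and f0 be the shares of unflagged I200 patients among users and comparators, and r their mortality ratio. Without any other adjustment, the risk ratio is multiplied by (1 + f1(r − 1)) / (1 + f0(r − 1)). All inputs are assumptions.

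- f1 = 2%, f0 = 1%, r = 1.5: 1.010 / 1.005 = 1.005.
- f1 = 5%, f0 = 3%, r = 2: 1.05 / 1.03 = 1.02.
- With f0 = 0 the same f1 and r give 1.01 and 1.05, an upper end for those inputs.

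**Step 5: comparison with sampling error.** Take 4% mortality in both groups, with no weighting. Users: 7,515 × 0.17 = 1,278, with 51 deaths. The remaining 83%: 6,237, with 249 deaths. The standard error of log RR is √(1/51 − 1/1,278 + 1/249 − 1/6,237) ≈ 0.150, so the 95% interval spans a factor of exp(1.96 × 0.150) ≈ 1.34 each way.

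**The case against.** The best defence is that the protocol does not say how the subgroup and the restriction will be coded. Only the propensity score and the test-negative models cite the Appendix. A programmer who follows the words of section 4.9 would remove unstable angina, and an analysis plan not shown here may list the codes. This stands: a reader might infer that the subgroup as coded retains unstable angina, but the protocol supports that only on the condition that the stable-angina rows are used.

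A reader might also infer that every I200 patient counts as free of coronary disease, or that any I200 cancels a PCI. Neither is supported. An I21-I23 code in the look-back sets the infarction flag, and an I200 recorded only after a procedure leaves the procedure flag in place.

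Third, other covariates partly stand in for the missing one: statins, aspirin, heart failure, loop diuretics and the other antihypertensives. The subgroup also drops patients with diabetes, renal disease, infarction or heart failure, some of whom have I200. In addition, section 4.8.1 relies first on propensity scores and the active comparator, with restriction as a further step, and admits that confounding by severity may remain. All of this reduces the likely size. None of it gives I200 a place in the list that the models are told to use.

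**Conclusion.** The gap in the covariate list is definite. With the table as written, a patient with I200, no I21-I23 code and no other coronary code has no coronary flag in the propensity score or the test-negative models, and this does not depend on how exclusion codes are read. Under the more natural patient-level reading it extends to patients who also carry I209 or I251. That I200 denotes unstable angina is the standard ICD-10 meaning; the protocol does not spell it out.

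For the subgroup and the restriction, the conclusion is narrower: text and table do not match and must be reconciled.

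The size cannot be derived from the protocol. On the assumptions shown, the bias is small beside the sampling error and beside the RR of 1.2 that section 4.10 aims to detect. A claim that the risk ratio is inflated by 1% to 5% would go too far: it needs almost no I200 among comparators and ignores the proxy covariates. The direction against CCB users is also unknown. The point merits correction because the error is systematic and easy to remove, not because it is likely to change the result.

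**What to change.** - Add I200 as a covariate of its own, or add it to the infarction row and relabel that row acute coronary syndrome (I200, I21-I23). Enter it in the propensity score and in both test-negative models.
- In section 4.9, state the codes that define the angina and infarction exclusions. In section 4.8.1, do so for the coronary part of heart disease. In both, use all of I20 (including I200), I251, I259, I21-I23 and the CABG/PCI procedures, with no exclusion codes. The stable-angina rows can stay as they are for use as covariates.
- State whether the exclusion column acts on the patient or only on the code.

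The cost is one or two table rows and a sentence in each section, using diagnosis and procedure data from a registry that the study already draws on. The uncomplicated-hypertension subgroup and the restricted population become slightly smaller.

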The risk of COVID-19 (a positive test for SARS-CoV-2) will be analyzed using a testnegative case-control design among all patients tested. All covariates will be tabulated for patients with a positive test and negative test for SARS-CoV-2. The odds ratio for current ACE-I/ARB use vs. non-use and CCB use, respectively, will be estimated using two separate logistic regression models adjusted for all covariates, see Appendix.

In a sensitivity analysis, we will explore the robustness of our findings by repeating the analyses in patients who filled a prescription within 120 days before a positive test.

Finally, we will do a sensitivity analysis stratified by calendar time to address changes in testing and hospitalization strategy.

10

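### Diabetes severity is incompletely adjusted: one covariate pools insulin, other glucose-lowering drugs and complication codes, so current insulin use, retinopathy and neuropathy are not balanced in the main analyses

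*Protocol*

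**What the plan says.** The Codes table at the end of the protocol lists diabetes as one covariate with no sub-rows. Its diagnosis part is "E10, E11, E12, E13, E14, O24, G63.2, H360, N083" (O24.4 excluded) and its drug part is A10A and A10B together. Both parts look back 10 years.

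Section 4.8.1.1 estimates the propensity score by a "logistic regression model including calendar time and the covariates listed in the Appendix". Section 4.9 estimates the test-negative odds ratios from "two separate logistic regression models adjusted for all covariates, see Appendix". The same list therefore governs both parts of the study.

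Other rows bear on diabetes severity. The kidney disease row ends with "Q61, N08, E102, E112, E142", which brings in diabetic renal codes. There is a separate row for "End-stage renal disease (kidney transplant or dialysis". Angina with and without procedures, myocardial infarction, heart failure, stroke, obesity, statins, aspirin and loop diuretics also have their own rows.

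Section 4.8.1 says that "we cannot exclude the impact of unmeasured confounding, e.g., by severity of condition indication ACE-I/ARB treatment". Where it becomes specific, it names two diseases only: "As we lacked detailed data on severity of heart and renal diseases".

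**The concern.** Section 2 names diabetes among the conditions often treated with ACE-I/ARB, and section 4.9 excludes diabetics when it isolates hypertension as the main indication. The protocol thus treats diabetes as bound up with the indication. If patients with more advanced diabetes are steered towards ACE-I/ARB rather than CCB, or rather than no such drug, and also die more often of COVID-19, then balancing a pooled diabetes variable leaves an imbalance inside the diabetic stratum. A patient with one tablet fill nine years ago and a patient now on insulin with retinopathy count as the same.

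The balance check would not reveal this. Section 4.8.1.1 plans standardized differences for the covariates. A pooled diabetes variable can look well balanced while insulin use within it is not.

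The separating information is already in hand. A10A is distinct from A10B, and G63.2 (neuropathy) and H360 (retinopathy) are distinct from the general diabetes codes. Statins, aspirin and loop diuretics each have a 90-day row of their own. Insulin appears only inside the 10-year diabetes definition.

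**Working it through.** **Step 1. What is and is not adjusted for.** The plan gives no figure on this point, so the check begins with the covariate list.

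| Aspect of diabetes severity | Where it enters |
|---|---|
| Nephropathy (N083, E102, E112, E142) | Kidney disease row (N08 contains N083) |
| Dialysis, kidney transplant | End-stage renal disease row |
| Coronary disease, heart failure, stroke | Separate rows |
| Obesity, statins, aspirin, loop diuretics | Separate rows |
| Current insulin versus other drugs | Only inside the pooled row |
| Retinopathy (H360), neuropathy (G63.2) | Only inside the pooled row |
| Diabetes type (E10 versus E11 and others) | Only inside the pooled row |
| Duration, glycaemic control | No listed measure |

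Ever/never coding is inferred from the layout. No levels are given for diabetes, whereas the row for number of antihypertensives states 0-5.

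**Step 2. Size of a residual bias, by assumption.** Let D be the share of diabetics in both weighted groups, s1 and s0 the severe share among diabetics in ACE-I/ARB users and comparators, R the mortality ratio of severe to non-severe diabetes, and RD the mortality ratio of non-severe diabetes to no diabetes. If nothing else absorbs the difference, the spurious risk ratio is

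[(1-D) + D·RD·(1+s1(R-1))] / [(1-D) + D·RD·(1+s0(R-1))].

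The documents supply none of these inputs.

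- *Low end:* D = 0.10, s1 = 0.30, s0 = 0.20, R = 1.3, RD = 1.0. (0.9 + 0.1 × 1.09)/(0.9 + 0.1 × 1.06) = 1.009/1.006 = 1.003.
- *High end:* D = 0.30, s1 = 0.50, s0 = 0.25, R = 2.0, RD = 1.5. (0.7 + 0.45 × 1.5)/(0.7 + 0.45 × 1.25) = 1.375/1.2625 = 1.089.
- *Intermediate set:* D = 0.35, s1 = 0.45, s0 = 0.30, RD = 1. With R = 1.5, 1.07875/1.0525 = 1.025. With R = 2, 1.1575/1.105 = 1.048.
- *Intermediate set with D = 0.20:* 1.045/1.03 = 1.015 with R = 1.5, and 1.09/1.06 = 1.028 with R = 2.

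If channelling ran the other way, the factors would fall below 1. The formula concerns mortality and says nothing about the test-negative odds ratio.

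**Step 3. Two yardsticks from section 4.10.**

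- *Target effect, RR 1.2:* on the log scale, 1.025 is 0.0246/0.1823 = 14% of it, 1.048 is 0.0464/0.1823 = 25%, and the extreme 1.089 is 0.0854/0.1823 = 47%.
- *Sampling error:* 7,515 test-positive patients, 17% and 7% users, and 4% mortality taken as equal everywhere give 7,515 × 0.17 × 0.04 = 51 deaths in ACE-I/ARB users, 7,515 × 0.07 × 0.04 = 21 in CCB users, and 7,515 × 0.83 × 0.04 = 249 in everyone not using ACE-I/ARB. Treating the groups as disjoint and ignoring weighting, the SE of log RR is about √(1/51 + 1/21) = 0.26 against CCB and √(1/51 + 1/249) = 0.15 against the rest. A factor of 1.05 (log 0.049) is then about 0.2 and 0.3 SE.

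**The case against.** The strongest reply is that nothing is misstated. The table is a code list. It says which codes identify diabetes, not how the variable is parameterised, and a SAP, which is not among the documents, could split it. Ever/never comorbidity covariates are ordinary practice, and a finer split could be asked of almost any row. This stands to the extent that the point is a refinement of the covariate set and not an error.

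A reader might infer that diabetes severity is left wholly unadjusted. The documents do not support that, because the renal and macrovascular rows carry part of it. Nor is the diabetes-free subgroup the only check. The section 4.8.1 restriction to patients without heart or kidney disease also removes diabetics with those coded conditions.

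A reader might also infer that section 4.8.1 contradicts the table by calling measured severity unmeasured. It does not. The concession is general, and the sentence about lacking severity data names heart and renal disease only.

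The size and direction of the bias are indeed assumed, and a few per cent is small against the expected sampling error. That limits the weight of the point. It does not remove the reason to use baseline information already extracted, since bias does not shrink as the cohort grows.

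**Conclusion.** The point holds as a modest improvement. Diabetes severity is incompletely adjusted in the main analyses because current insulin use, retinopathy and neuropathy enter only through one pooled covariate, apparently ever/never over 10 years. The two restricted analyses are partial checks. The first retains diabetics without coded heart or kidney disease, and the second answers the question in a different population.

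Under assumed inputs the residual bias factor on the mortality risk ratio lies between about 1.00 and 1.09, with 1.02 to 1.05 for the intermediate set at 35% diabetics. These are upper illustrations, because the formula gives no credit to the renal and cardiovascular covariates. An upward direction rests on the assumption that more severe diabetics are channelled towards ACE-I/ARB, which the documents do not show.

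**What to change.** Keep the diabetes covariate and add two indicators built from codes already listed:

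1. Insulin (A10A) filled within 90 days before the test, matching the window used for the other co-medications.
2. Any non-renal diabetic complication code (G63.2 or H360) within 10 years. State whether further E10-E14 complication subcodes count.

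Enter both in the propensity score for each comparison, in the table of standardized differences and in the test-negative models. Keep them separate and do not pool them into one severe category. Insulin also marks type 1 diabetes, and a pooled category would put uncomplicated type 1 together with complicated type 2.

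The cost is two parameters per model and slightly more variable weights, mainly in the smaller CCB group. No new data are needed and the estimand is unchanged. If the sponsor expects little effect, the balance table will show whether that is so.
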